13.4.2 Audits and Inspections

A quality assurance audit may be performed at any time by the Sponsor's Clinical Quality Assessment department (CQA) or by independent auditors to verify that the study has been conducted according to the protocol, GCP and ICH requirements, and other applicable regulations. An inspection may be conducted by regulatory authorities. The Investigator must allow direct access to study documents during these inspections and audits.

13.4.3 Archiving

The Investigator must keep all study documents after the completion or discontinuation of the study, whatever the nature of the investigational center (private practice, hospital, or institution), for as long as required by applicable laws and regulations. In the absence of any applicable laws or regulations, study documents will be kept at a minimum for the duration indicated on the Clinical Trial Agreement (CTA). In no event, should study personnel destroy or permit the destruction of any study documents upon less than 90 days advance written notification to the Sponsor. In addition, study documents should continue to be stored, at Sponsor's sole expense, in the event that the Sponsor requests in writing that such storage continues for a period of time that exceeds that required by any applicable law or regulation or the CTA. The Investigator will inform Sanofi Pasteur of any address change or if they will no longer be able to house the study documents.

Archived data may be held on electronic records, provided that a back-up exists and that a hard copy can be obtained if required. The protocol, documentation, approvals, and all other documents related to the study will be kept by the Sponsor in the Trial Master File (TMF). Data on AEs are included in the TMF. All data and documents will be made available if requested by relevant authorities.

13.5 Financial Contract and Insurance Coverage

A CTA will be signed by all the parties involved in the study's performance, if relevant. The Sponsor has an insurance policy to cover any liabilities that may arise from use of the product and / or the study protocol.

13.6 Stipends for Participation

Subjects may be provided with a stipend according to local practice to compensate for the time and travel required for study visits and procedures.

Invasive meningococcal disease (IMD) is a serious illness caused by the bacterium *Neisseria meningitidis* (*N. meningitidis*), a Gram-negative diplococcus found exclusively in humans. At least 12 distinct meningococcal serogroups have been classified based on the immunochemistry of the capsular polysaccharides (PS). The epidemiology of *N. meningitidis* can be described as complex, unpredictable, geographically variable, and changing over time. Meningococcal disease occurs worldwide in both endemic and epidemic forms with seasonal variation.

Every year more than 2 million people from all over the world undertake the Hajj, the annual pilgrimage to Mecca. The Hajj is an epidemiological phenomenon. Because of crowds, high humidity, and air pollution, the carriage rate of *N. meningitidis* can be as high as 80% which eventually may cause epidemics.

Epidemics during the Hajj have been known for decades. After the first documented international outbreak caused by serogroup A, vaccination was mandated for pilgrims to enter the Kingdom of Saudi Arabia (KSA). Starting in 2002, following serogroup-W outbreaks in 2000 and 2001, the requirement for vaccination with bivalent AC vaccine was switched to quadrivalent (ACYW) polysaccharide vaccine (29). Visitors arriving for the purpose of Umrah or pilgrimage (Hajj) are required to submit a certificate of vaccination with the tetravalent (ACYW) vaccine against meningitis, proving the vaccine was administered no less than 10 days before arrival in KSA. Both polysaccharide and conjugate vaccines are valid options.

The goal for MenACYW conjugate vaccine is to provide broad protection against invasive meningococcal disease (IMD) caused by serogroups A, C, W, and Y in all age groups including children as young as 6 weeks of age, adolescents, and adults, including those 56 years of age and older.

MenACYW conjugate vaccine was found to be well tolerated and no unanticipated or new significant safety concerns have been identified in the clinical trials completed to date or in the ongoing studies.

The KSA has a long history of instituting preventative measures against meningococcal disease. KSA is at risk of outbreaks of meningococcal disease due to its geographic location, demography, and especially because it hosts the annual Hajj and Umrah mass gatherings.

The mandatory meningococcal vaccination policy for pilgrims has possibly been the major factor in preventing outbreaks during the pilgrimages and has also probably been important in reducing the carriage and transmission of *Neisseria meningitidis* in KSA and beyond. The preventative measures for Hajj and Umrah favor the conjugate vaccine for its extra benefits over the polysaccharide vaccines. The Hajj in 2012 and 2013 attracted more than 5 million pilgrims from 184 countries. Most of these pilgrims are part of the elderly population.

2 Trial Objectives

Immunogenicity

- To describe the antibody response to meningococcal serogroups A, C, W, and Y measured by serum bactericidal assay using baby rabbit complement (rSBA) before and 30 days (+14 days) after a single dose of MenACYW conjugate vaccine
- To describe the antibody response to meningococcal serogroups A, C, W, and Y measured by serum bactericidal assay using human complement (hSBA) before and 30 days (+14 days) after a single dose of MenACYW conjugate vaccine
- To describe the antibody responses against tetanus toxoid at baseline and 30 days (+14 days) after a single dose of MenACYW conjugate vaccine

Safety

- To describe the safety profile of a single dose of MenACYW conjugate vaccine

3 Description of the Overall Trial Design and Plan

3.1 Trial Design

This is a Phase III, open-label, study to describe the immunogenicity and safety of MenACYW conjugate vaccine in potential pilgrims \geq 56 years of age in Turkey and Lebanon.

Approximately 330 healthy adults were to be enrolled in the study to receive a single dose of MenACYW conjugate vaccine.

All subjects will provide pre-vaccination blood samples for immunogenicity assessment at baseline (Visit 1) and at Day (D) 30 (+14-day window) post-vaccination (Visit 2).

Safety data were to be collected as follow: Immediate unsolicited systemic adverse events (AEs) were to be collected within 30 minutes after vaccination. Solicited AE information was to be collected for 7 days after vaccination, unsolicited AE information was to be collected from Visit 1 to Visit 2, and SAE information (including adverse events of special interest [AESIs]) was to be collected from Visit 1 through Visit 2.

A certificate of vaccination was to be given to each subject after vaccination. The individual subject immunogenicity results were to be made available to the study Investigator once they are available. The Investigator was to communicate the study results to the individual subjects. Any subsequent clinical intervention, if needed, were to be the responsibility of the Investigator based on his/ her clinical judgement and outside of the scope of this protocol. If the antibody titers against meningococcal serogroups A, C, W, and Y measured by rSBA did not reach the protective titer of \geq 1:8 for one of the serogroups included in the vaccine, the Investigator was to advise whether, in light of a potential pilgrimage for Hajj or Umrah in the following 5 years, vaccination with a licensed quadrivalent meningococcal conjugate vaccine was necessary.

3.2 Trial Plan

A schedule of assessments and study vaccinations is provided in [Table 3.1](#).

Vaccination

All subjects will receive a single dose of MenACYW conjugate vaccine at Visit 1 (D0).

Blood Sampling

All subjects will provide a pre-vaccination blood sample at Visit 1 and a post-vaccination sample at Visit 2 (30 to 44 days after the vaccination at Visit 1).

Collection of safety data

- All subjects will be followed for safety from Visit 1 (D0) to Visit 2.
- All subjects will be observed for 30 minutes after vaccination, and any unsolicited systemic AEs occurring during that time were to be recorded as immediate unsolicited systemic AEs in the case report book (CRB).
- The subject will record information in a diary card about solicited reactions from D0 to D07 after vaccination and unsolicited AEs from D0 to Visit 2.
- SAEs (including AESIs) will be recorded throughout the duration of the trial. The subject will record information in a diary card about SAEs from D0 to Visit 2.
- The subject will be asked to notify the site immediately about any potential SAEs at any time during the trial.
- Staff will also contact subjects by telephone on D08 (+2 days) to identify the occurrence of any SAE not yet reported and to remind them to complete the diary card up to Visit 2 and to bring it back to Visit 2.
- The completed diary card will be reviewed with the subject at Visit 2.

Table 3.1: Study procedures

Phase III Trial, 2 Visits, 1 Vaccination, 2 Blood Samples, 1 Telephone Call,
30 to 44 Days duration per Subject

Visit/Contact	Visit 1	Telephone Call	Visit 2
Trial timelines (days)	D0	D08	D30
Time windows (days)	NA	+2 days	+14 days
Informed consent	X		
Inclusion/exclusion criteria	X		
Collection of demographic data	X		
Urine pregnancy test (if applicable)	X		
Medical history	X		
Physical examination*	X		
Allocation of subject number	X		
Review of temporary contraindications for blood sampling †			X
Blood sampling (BL), 10 mL‡§	BL0001		BL0002
Vaccination	X		
Immediate surveillance (30 min)	X		
Diary card provided	X		
Telephone call		X§	
Recording of solicited injection site & systemic reactions	D0 to D07		
Recording of unsolicited non-serious AEs		D0 to Visit 2	
Diary card reviewed and collected			X
Reporting of SAEs (including AESIs)**		To be reported throughout the study period	
Collection of reportable concomitant medications	X		X
Trial termination record			X

* Temperature needs to be measured and recorded in source documents.

† Should a subject receive oral or injectable antibiotic therapy within 3 days prior to the second blood draw, the Investigator was to postpone that blood draw until it has been 3 days since the subject last received oral or injectable antibiotic therapy. Postponement must still be within the timeframe for blood draw (30 to 44 days after vaccination at Visit 1). If postponement would result in the sample collection falling outside of this timeframe, the blood sample should be collected without postponement, and it should be documented appropriately that the sample was taken less than 3 days after stopping antibiotic treatment.

‡ A pre-vaccination blood sample was to be collected from all subjects at D0.

§ This call is made 8 to 10 days after the vaccinations on D0. If D08 (+2 days) falls on a weekend or holiday, the telephone call may be made on the following business day. During this telephone call, the staff was to find out whether the subject experienced any SAE not yet reported, and was to remind the subject to continue using the diary card up to Visit 2, to bring the diary card to the study center at Visit 2, and confirm the date and time of Visit 2.

** AESIs were to be collected throughout the trial as SAEs to ensure that the events are communicated to the Sponsor in an expedited manner and followed up until the end of the follow-up period or resolution, as per the assigned causality.

4 Endpoints and Assessment Methods

4.1 Immunogenicity

The endpoints for the evaluation of immunogenicity are:

- Antibody titers $\geq 1:8$ against meningococcal serogroups A, C, W, and Y measured by rSBA assessed at 30 days (+14 days) after vaccination with a single dose of MenACYW conjugate vaccine
- Antibody titers against meningococcal serogroups A, C, W, and Y measured by rSBA before and 30 days (+14 days) after vaccination with MenACYW conjugate vaccine
- Antibody titers against meningococcal serogroups A, C, W, and Y measured by hSBA before and 30 days (+14 days) after vaccination with MenACYW conjugate vaccine
- Tetanus toxoid is contained in the investigational vaccine as a carrier protein. Therefore, blood samples will also be tested for anti-tetanus antibodies by electrochemiluminescence (ECL).

The following endpoints will be assessed:

- Antibody concentrations to tetanus toxoid at both pre- and post-vaccination time points, geometric mean concentrations (GMCs)
- The proportion of subjects achieving seroprotective levels ≥ 0.01 International Units (IU) /milliliters (mL) and ≥ 0.1 IU/mL of antibody concentrations to tetanus toxoid at both pre- and post-vaccination time points

See section 9.1.1 of the protocol for the description of the immunogenicity assessment methods used.

4.2 Safety

The following endpoints will be used for all subjects for the evaluation of safety:

- Unsolicited systemic AEs reported in the 30 minutes after the vaccination, including occurrence, nature (Medical Dictionary for Regulatory Activities [MedDRA] preferred term), duration, intensity, relationship to the product administered, and whether the event caused termination from the study.
- Solicited (prelisted in the subject's diary card and CRB) injection site and systemic reactions starting any time from Day 0 (day of vaccination) through Day 7 after the vaccination, including occurrence, time of onset, number of days of occurrence, intensity, action taken, and whether the reaction caused termination from the study.
- Unsolicited AEs occurring up to Visit 2, including occurrence, nature (MedDRA preferred term), time of onset, duration, intensity, action taken, relationship to the product administered (for systemic AEs only), and whether the event caused termination from the study.

- SAEs (including AESIs) reported throughout the trial, including occurrence, nature (MedDRA preferred term), time of onset, duration, seriousness criteria, relationship to the product administered, whether the event caused termination from the study, outcome.

See Section 9.2 of the protocol for more details.

[Table 4.1](#) and [Table 4.2](#) present, respectively, the injection site reactions and systemic reactions that are prelisted in the diary cards and CRB, together with the intensity scales.

Table 4.1: Solicited injection site reactions: terminology, definitions, and intensity scales

CRB term (MedDRA lowest level term [LLT])	Injection site pain	Injection site erythema	Injection site swelling
MedDRA preferred term (PT)	Injection site pain	Injection site erythema	Injection site swelling
Diary card term	Pain	Erythema	Swelling
Definition	Pain either present spontaneously or when the injection site is touched or injected limb is mobilized	Presence of a redness including the approximate point of needle entry	Swelling at or near the injection site. Swelling or edema is caused by a fluid infiltration in tissue or cavity and, depending on the space available for the fluid to disperse, swelling may be either soft (typically) or firm (less typical) to touch and thus can be best described by looking at the size of the swelling.
Intensity scale*	Grade 1: A type of adverse event that is usually transient and may require only minimal treatment or therapeutic intervention. The event does not generally interfere with usual activities of daily living. Grade 2: A type of adverse event that is usually alleviated with additional therapeutic intervention. The event interferes with usual activities of daily living, causing discomfort but poses no significant or permanent risk of harm to the research participant. Grade 3: A type of adverse event that interrupts usual activities of daily living, or significantly affects clinical status, or may require intensive therapeutic intervention.	Grade 1: ≥ 25 to ≤ 50 mm Grade 2: ≥ 51 to ≤ 100 mm Grade 3: > 100 mm	Grade 1: ≥ 25 to ≤ 50 mm Grade 2: ≥ 51 to ≤ 100 mm Grade 3: > 100 mm

* For the subjective reaction of pain, subjects will record the intensity level (Grade 1, 2, or 3) in the diary card. For the measurable reactions of redness and swelling, they will record just the size of the reaction, and the classification as Grade 1, 2, or 3 will be assigned at the time of the statistical analysis

Table 4.2: Solicited systemic reactions: terminology, definitions, and intensity scales

CRB term (MedDRA LLT)	Fever	Headache	Malaise	Myalgia
MedDRA PT	Pyrexia	Headache	Malaise	Myalgia
Diary card term	Temperature	Headache	Feeling unwell	Muscle aches and pains
Definition	Elevation of temperature to $\geq 38.0^{\circ}\text{C}$ ($\geq 100.4^{\circ}\text{F}$)	Pain or discomfort in the head or scalp. Does not include migraine.	General ill feeling. Malaise is a generalized feeling of discomfort, illness, or lack of well-being that can be associated with a disease state. It can be accompanied by a sensation of exhaustion or inadequate energy to accomplish usual activities.	Muscle aches and pains are common and can involve more than one muscle at the same time. Muscle pain can also involve the soft tissues that surround muscles. These structures, which are often referred to as connective tissues, include ligaments, tendons, and fascia (thick bands of tendons). Does not apply to muscle pain at the injection site which should be reported as injection site pain.
Intensity scale*	Grade 1: $\geq 38.0^{\circ}\text{C}$ to $\leq 38.4^{\circ}\text{C}$, or $\geq 100.4^{\circ}\text{F}$ to $\leq 101.1^{\circ}\text{F}$ Grade 2: $\geq 38.5^{\circ}\text{C}$ to $\leq 38.9^{\circ}\text{C}$, or $\geq 101.2^{\circ}\text{F}$ to $\leq 102.0^{\circ}\text{F}$	Grade 1: A type of adverse event that is usually transient and may require only minimal treatment or therapeutic intervention. The event does not generally interfere with usual activities of daily living. Grade 2: A type of adverse event that is usually alleviated with additional therapeutic intervention. The event interferes with usual activities of daily living, causing discomfort but poses no significant or permanent risk of harm to the research participant.	Grade 1: A type of adverse event that is usually transient and may require only minimal treatment or therapeutic intervention. The event does not generally interfere with usual activities of daily living. Grade 2: A type of adverse event that is usually alleviated with additional therapeutic intervention. The event interferes with usual activities of daily living, causing discomfort but poses no significant or permanent risk of harm to the research participant.	Grade 1: A type of adverse event that is usually transient and may require only minimal treatment or therapeutic intervention. The event does not generally interfere with usual activities of daily living. Grade 2: A type of adverse event that is usually alleviated with additional therapeutic intervention. The event interferes with usual activities of daily living, causing discomfort but poses no significant or permanent risk of harm to the research participant.

CRB term (MedDRA LLT)	Fever	Headache	Malaise	Myalgia
	Grade 3: $\geq 39.0^{\circ}\text{C}$ or $\geq 102.1^{\circ}\text{F}$	Grade 3: A type of adverse event that interrupts usual activities of daily living, or significantly affects clinical status, or may require intensive therapeutic intervention.	Grade 3: A type of adverse event that interrupts usual activities of daily living, or significantly affects clinical status, or may require intensive therapeutic intervention.	Grade 3: A type of adverse event that interrupts usual activities of daily living, or significantly affects clinical status, or may require intensive therapeutic intervention.

* For all reactions but fever, subjects will record the intensity level (Grade 1, 2, or 3) in the diary card. For fever, they will record the body temperature, and the classification as Grade 1, 2, or 3 will be assigned at the time of the statistical analysis based on the unit used to measure the temperature and the intensity scale.

4.3 Derived Endpoints: Calculation Methods

4.3.1 Safety

4.3.1.1 Solicited Reactions

4.3.1.1.1 Daily Intensity

All daily records for solicited reactions will be derived into daily intensity according to the following classification: None, Grade 1, Grade 2, Grade 3, or Missing (Unknown).

For the derivation of daily intensities the following sequential steps will be applied:

- 1) Solicited reactions (except Fever/Pyrexia) with CRF presence recorded as “No” and with all daily records missing (Unknown) then all daily intensities will be derived as None.
- 2) For non-measurable solicited reactions, daily intensities will correspond to daily records reported in the clinical database. For measurable solicited reactions the daily measurements reported in the clinical database will be converted based upon the intensity scales defined in the protocol; this assumes a reaction that is too large to measure (non measurable, “NM”) is Grade 3. Note the intensity could be considered “None” (not a reaction) in the analysis despite being considered a reaction by the investigator (e.g., swelling measurement > 0 mm but < 25 mm in adults).

Note: The maximum intensity on the ongoing period is derived from the record of the maximum intensity/measurement after the end of the solicited period following the rule described above.

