13.2 Source Data and Source Documents

“Source data” are the data contained in source documents. Source documents are original documents or certified copies, and include, but are not limited to, diary cards, medical and hospital records, screening logs, informed consent / assent forms, telephone contact logs, and worksheets. The purpose of study source documents is to document the existence of subjects and to substantiate the integrity of the study data collected. Investigators must maintain source documents so that they are accurate, complete, legible, and up to date.

For missing or discrepant data on a diary card, the study coordinator will obtain verbal clarification from the subject, enter the response into the “investigator’s comment” page of the diary card, and transfer the information to the CRB.

The subject pre-screening log should list all individuals contacted by the Investigators to participate in the study, regardless of the outcome.

If electronic medical records are used, the Investigator must print^a any electronic records on an ongoing basis, sign and date them immediately after creation, and keep the printouts on file as

^a Unless the electronic medical records are managed by validated computerized systems that are compliant with US 21 CFR Part 11, in which case they are acceptable on their own.

source documents that can be verified by the Sponsor or an inspector against the electronic records. Any subsequent changes of an electronic record require the record to be re-printed, dated (with an indication of the date of change), and signed. Such records must also be kept together with the original printed copy.

Good Documentation Practice should be followed by the Investigator and the site staff managing source documents.

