4.3.1.1.3 Presence

Presence is derived from the maximum overall intensity over the time period considered:

- None: No presence
- Grade 1, Grade 2, or Grade 3: Presence
- Missing or Unknown: Missing presence

Subjects with at least one non-missing presence for a specific endpoint will be included in the analysis. Conversely, those without a non-missing presence will not be included in the analysis of the endpoint.

The time period is displayed as D0-D3, D4-D7, D8 and later.

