5.3 Handling of Missing Data and Outliers

5.3.1 Safety

No replacement will be done. In all subject listings, partial and missing data will be clearly indicated as missing.

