5.3.1.3 Intensity

For solicited reactions, missing intensities will be handled as described in [Section 4.3.1.1.1](#). For unsolicited AEs, missing intensities will remain missing and will not be imputed.

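### With no daily records, a solicited reaction answered No on the CRF is kept as a non-reaction, but one answered Yes drops out, which lowers the reported rates of pain, headache, malaise and myalgia

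*SAP*

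**What the plan says.** Solicited reactions are graded from daily diary entries for D0 to D07 (Protocol 9.2.3.2). SAP 4.3.1.1.1 turns the entries into daily intensities in two ordered steps.

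- **Step 1** uses the CRF presence answer in one situation only. It covers reactions other than fever "with CRF presence recorded as “No” and with all daily records missing (Unknown) then all daily intensities will be derived as None".
- **Step 2** covers everything else. "For non-measurable solicited reactions, daily intensities will correspond to daily records reported in the clinical database". For measurable reactions, the recorded measurement is converted with the intensity scale. A size above 0 but under 25 mm may become None, even if the investigator regarded it as a reaction.

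SAP 4.3.1.1.3 then says: "Presence is derived from the maximum overall intensity over the time period considered". Presence therefore comes from the grades and not from the CRF answer. A missing maximum gives a missing presence, and "those without a non-missing presence will not be included in the analysis of the endpoint".

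The missing-data sections add no further rule. SAP 5.3.1.3 says "For solicited reactions, missing intensities will be handled as described in" SAP 4.3.1.1.1, and SAP 5.3.1 says "No replacement will be done. In all subject listings, partial and missing data will be clearly indicated as missing".

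**The concern.** The same CRF field is used when it says No and has no effect when it says Yes. Take two subjects with no daily headache record. One reports no headache and is analysed as a non-reactor. The other reports a headache but cannot grade it by day, and is removed from both numerator and denominator. Among subjects without daily records, those who deny a reaction stay in and those who confirm one go out. Solicited reaction rates are a stated safety endpoint (Protocol 9.2.2, SAP 4.2), so the loss falls directly on a reported result.

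The SAP treats the parallel case differently. For intensity it says "For unsolicited AEs, missing intensities will remain missing and will not be imputed", but under SAP 4.3.1.2.1 an unsolicited event counts if it has a verbatim term and is not Grade 0. A missing grade does not remove it. SAP 4.3.1.5.6 shows the same contrast for events leading to discontinuation. In the SOC/PT table an unsolicited event may have a missing grade, while a solicited one needs at least Grade 1.

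The situation is plausible. The telephone call around D08 reminds subjects to complete the diary, but the diary is reviewed with them only at Visit 2, 30 to 44 days after vaccination (Protocol 5.1.3 and 5.1.4). By then a subject may remember a headache without remembering its grade on each day.

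**Working it through.** The plan gives no figure on this point, so there is none to reproduce. The check traces the rule and then sizes its effect.

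**Tracing the rule when all daily records for a reaction are missing**

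| CRF presence | Daily intensity (4.3.1.1.1) | Presence (4.3.1.1.3) | In the analysis? |
|---|---|---|---|
| No | None on every day (step 1) | No presence | Yes, as non-reactor |
| Yes | Missing on every day (step 2 has nothing to carry over) | Missing | No |

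The second row is not written out in the SAP. It is what the stated steps give when followed in order.

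**Inputs**

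- N = 290 subjects enrolled (SAP 5.7.2). This is the upper limit of the safety denominator.
- R = number of true reactors. Assumed as 10%, 30% or 50% of N, that is 29, 87 or 145.
- m = number of reactors with presence Yes and no daily record. The documents do not give it. It is assumed as 1, 3 or 6, with 15 as a deliberately high value.

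**Formula for a subjective reaction**

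Rate with these subjects counted: R/N. Rate under the SAP: (R − m)/(N − m). The difference is

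(R − m)/(N − m) − R/N = −m(N − R) / [N(N − m)],

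which is negative whenever m > 0 and R < N.

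For R = 87 and m = 6: 81/284 = 28.52% against 87/290 = 30.00%. By the formula, −6 × 203/(290 × 284) = −1.48 percentage points.

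| m | True rate 10% | True rate 30% | True rate 50% |
|---|---|---|---|
| 1 | 9.69% | 29.76% | 49.83% |
| 3 | 9.06% | 29.27% | 49.48% |
| 6 | 8.10% | 28.52% | 48.94% |
| 15 | 5.09% | 26.18% | 47.27% |

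At a true rate of 30% and m = 6, the Clopper-Pearson 95% interval moves from 24.8–35.6% to 23.3–34.2%.

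**Erythema and swelling**

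Here an unmeasured Yes need not be a reaction on the analysis scale. Assume 23 graded reactors and 6 unmeasured Yes answers among 290. The SAP reports 23/(290 − 6) = 8.10%.

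| Of the 6, number at least 25 mm | True rate | Bias (percentage points) |
|---|---|---|
| 6 | 29/290 = 10.00% | −1.90 |
| 3 | 26/290 = 8.97% | −0.87 |
| 0 | 23/290 = 7.93% | +0.17 |

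The sign depends on sizes that were never recorded.

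**The case against.** The strongest case on the other side has three parts.

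**The two answers are not logically equivalent.** A No for the whole period implies None on every day, while a Yes implies no particular grade on any day. A blank daily grid after No may also be routine form completion and not a lost diary; the CRF is not among the documents. This stands as a defence of step 1, and it means No answers should not be set to missing for the sake of symmetry. That could remove ordinary non-reactors and inflate the rates. It does not justify losing the Yes: the grade is unknown, but presence is known.

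**The record should be rare.** Investigator assessment of solicited reactions is mandatory (Protocol 9.2.1). Staff interview subjects to clarify incomplete entries, and the investigator must explain missing information (Protocol 11.1). Computerized checks look for omissions (Protocol 11.2). Protocol 13.2 adds: "For missing or discrepant data on a diary card, the study coordinator will obtain verbal clarification from the subject". This stands and limits the likely size. It does not supply a rule for the records that remain.

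**The study is descriptive, and the shifts are small beside the interval width.** This also stands. It bears on priority, not on whether the rule is one-sided.

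Three stronger readings are tempting and are not supported:

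- A reader might infer that anyone who stops the diary early is affected. Step 1 requires every daily record to be missing. A subject who graded a reaction on even one day has a non-missing maximum and counts as a reactor.
- A reader might infer that all solicited rates can only move down. Fever is outside step 1, and for erythema and swelling the direction is open.
- A reader might infer a sizeable bias by supposing that 5% to 15% of subjects lack daily records. Nothing in the documents supports such a share.

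**Conclusion.** The gap is real. Following the SAP as written, a subject who confirms pain, headache, malaise or myalgia but has no daily record is dropped from that endpoint, while a subject who denies it is kept. For these four reactions the reported rate falls whenever such a record exists, and no other section corrects it.

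The size is unknown and probably small. With 290 subjects and assumed true rates of 10% to 50%, one such subject costs about 0.2 to 0.3 percentage points, three cost 0.5 to 0.9, and six cost 1.1 to 1.9. These figures rest on the assumed counts, on treating each such Yes as a true reaction, and on 290 as the denominator. If no such record exists, nothing changes. The correction is still worth making, because the error runs in one direction in a stated safety endpoint and is cheap to remove.

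**What to change.** Add to SAP 4.3.1.1.1 and 4.3.1.1.3:

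- For injection site pain, headache, malaise and myalgia, CRF presence Yes with all daily records missing counts as presence. The subject enters the numerator and denominator of the row for any reaction. Intensity, time of onset and number of days are Missing, and the table shows a separate row for missing grade.
- For erythema and swelling, keep the current derivation, report the number of Yes answers without any measurement, and give a sensitivity count that includes them.
- Leave the step 1 treatment of No answers as it is.

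The cost is a short addition to the SAP and a small change to the derivation program and table layout. The downside for the sponsor is that some reported rates may be slightly higher.
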